- 13. Tumor (core needle) biopsy (Section 8.1.6) This assessment may occur during the Screening period, but must be performed after the Screening MRI volumetric assessment has been confirmed evaluable by central radiologic review and prior to first dose of study treatment. Tumor biopsy will be utilized for PD tumor response in participants ≥ 18 years of age. Participants 2 to 17 years of age should not undergo biopsy unless there is a clinical indication to obtain fresh tumor tissue. If a study biopsy was collected and the participant did not initiate study treatment, this biopsy may be utilized as the baseline biopsy if the participant subsequently re-screens for enrollment.
- 14. Ophthalmic assessments (Section 8.2.7) will include slit lamp with binocular indirect ophthalmoscopy and intraocular pressure measurements. Assessments must be performed by an ophthalmologist. Participants in the pediatric cohort must be evaluated by a pediatric ophthalmologist.
- 15. 12-Lead Electrocardiograms (ECGs) (Section 8.2.4) should be administered in triplicate (approximately 2-3 minutes apart and averaged) and read locally at the Site. Participants should rest in semi-recumbent supine position for at least 5 minutes prior to ECG collection.
 - 15a. At Cycle 1 Day 1, triplicate ECGs are required prior to the first dose of study treatment and approximately 1-hour post dose.
 - **15b.** At Cycle 1 Day 15, triplicate ECGs are required 1-hour post dose of study treatment with a ±10-minute allowed window.
 - 15c. Triplicate ECG may be conducted at any time during the visit after completion of applicable PROs.
- 16. Echocardiogram (Section 8.2.8): Left ventricular ejection fraction (LVEF) will be assessed via echocardiogram.
 - 16a. Echocardiogram required at Screening to confirm or re-confirm Exclusion Criterion 11 and will serve as the Baseline echocardiogram throughout the study.
 - **16b.** Echocardiogram at the ET visit only required if not performed within the past 1 month.
- 17. Strength assessment (Section 8.1.3) will be measured utilizing a dynamometer and Medical Research Council (MRC) Muscle Scale for participants with a target plexiform neurofibroma (PN) that causes motor dysfunction or weakness. The MRC grading assessment should be conducted prior to the dynamometer assessment. Must be done prior to first dose of study treatment at the Baseline visit. Strength assessment at the early termination (ET) visit only required if not performed within the past 1 month.

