- 4. Participant has a target PN that is deemed inoperable, defined as a PN that cannot be completely surgically removed without risk for substantial morbidity due to: encasement of or close proximity to vital structures, invasiveness, or high vascularity of the PN, or the participant refuses surgery. Participants who previously underwent surgery for a PN will be eligible to enter the study after the surgery, provided the PN was incompletely resected and is evaluable by volumetric analysis;
- 5. Participants must have a target PN, defined as the clinically most relevant PN, amenable to volumetric MRI analysis. For the purpose of this study, the target PN must be seen on at least 3 consecutive MRI slices and the field of view must contain the entire tumor of interest. As determined by central radiologic review, a target PN must be analyzable by volumetrics using the REiNS criteria, at least 5 mL in volume, and will be classified as "typical PN", "nodular PN", or "solitary nodular PN" prior to first dose of study treatment;
- 6. Participants ≥ 18 years of age must have a PN amenable to a percutaneous biopsy and must be willing to undergo pre-, and end of treatment tumor biopsies providing fresh tumor tissue; there should be no contraindication for serial biopsy; Participants 2 to 17 years of age should not undergo biopsy unless there is a clinical indication to obtain fresh tumor tissue;
- 7. Participants ≥ 16 years of age must have a Karnofsky performance level of $\geq 50\%$, and participants < 16 years must have a Lansky performance of $\geq 50\%$. Note: Participants who are unable to walk because of paralysis, but who are upright in a wheelchair, will be considered ambulatory for the purpose of assessing the performance score;
- 8. Participant has adequate organ and bone marrow function as defined by the following Screening laboratory values:
 - 8.1. Absolute neutrophil count $\geq 1500 \text{ cells/}\mu\text{L}$;
 - 8.2. Platelets $\geq 100 \text{ x } 10^3/\mu\text{L}$;
 - 8.3. Hemoglobin \geq 9.5 g/dL;
 - 8.4. Serum albumin $\geq 2.8 \text{ g/dL}$;

8.5. Calculated creatinine clearance at Screening ≥ 60 mL/min (by Cockcroft-Gault formula) OR a normal serum creatinine based on age described in the table below;

Age (years)	Maximum Serum Creatinine (mg/dL)
≤5	0.8
$>$ 5 and \leq 10	1.0
> 10 and ≤ 15	1.2
> 15	1.5

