Ophthalmic assessments (Section 8.2.7) must be performed by an ophthalmologist throughout the study. Participants in the pediatric cohort must be evaluated by a pediatric ophthalmologist. The Screening ophthalmic exam will reconfirm Exclusion Criterion 12.

For WOCBP, a serum pregnancy test will be conducted at Screening to confirm eligibility (Inclusion Criterion 13).

An echocardiogram (Section 8.2.8) is performed to confirm Exclusion Criterion 11.

Triplicate 12-Lead ECGs (Section 8.2.4) are performed to confirm Exclusion Criterion 9.

A practice 6-minute walk test (Section 8.1.7) must be conducted during Screening, if applicable for the participant.

Baseline and Cycle 1 Day 1

The Baseline visit may occur up to 48 hours prior to first dose of study treatment. However, the PRO assessments will begin 6 days prior to the first day of the Baseline visit. The PII and NRS-11 questionnaires will be completed using the home ePRO device daily for 6 consecutive days prior to the scheduled Baseline visit. At the Baseline visit, the following PRO assessments will be completed prior to all other study assessments to minimize participant bias in the clinic: (PedsQL [paper], PII, NRS-11, PROMIS and PGIS [Table 9]). The paper PedsQL should always be the first PRO administered at the visit.

Because the Baseline visit may occur over 48 hours, Cycle 1 Day 1 will be defined as the date of administration of the first dose of study treatment. The following Baseline assessments are to be conducted prior to the first dose of study treatment:

- PROs (to be completed prior to all other study assessments to minimize participant bias) (Section 8.1.2)
- Concomitant medication and AE/SAE review (Section 8.3);
- Urinalysis / urine pregnancy for WOCBP;
- Blood draw for hematology and serum chemistry (Section 8.2.5);
- Pre-dose PK blood draw (should be within 1 hour prior to dosing when possible) (Section 10.8);
- Vital signs (including height and weight) (Section 8.2.3);
- Pre-dose triplicate 12-Lead ECGs (Section 8.2.4);

- Physical examination and Karnofsky/Lansky performance status (Section 8.2.2)
- Range of motion assessment and strength assessment utilizing a dynamometer and Medical Research Council (MRC) Muscle Scale (for participants with a target PN that causes motor dysfunction or weakness) (Section 8.1.3 and 8.1.5), and should be conducted prior to lab draws if the range of motion or strength assessment may be affected by the lab draw;

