8.1.2.2. Numerical Rating Scale-11

The Numerical Rating Scale-11 (NRS-11) is a self-report segmented 11-point numeric scale that assesses pain severity over the past 24 hours. The NRS-11 will be administered over 7 consecutive days, inclusive of the study visit day, as described in the SoA (Section 1.3) during the Treatment Phase. For the ET visit, the assessment will only be conducted once at the Site and not for the preceding 6 days. Participants ≥ 8 years of age will be administered the NRS-11 as a

¹ Administered as a paper assessment. The paper PedsQL should always be the first PRO administered at the visit.

² If a participant is ≥ 18 years of age, but in the opinion of the investigator has cognitive deficiencies that would inhibit accurate collection of PRO data, a parent or legal guardian must also complete the appropriate parent-proxy PRO

³ Administered as a paper assessment. This assessment will only be completed once during the study for participants utilizing the dispersible tablet dosage form.

self-report. Participants are asked to select the one number from 0 to 10 that best describes their worst pain over the past 24 hours for target tumor pain with 0 representing "no pain" and 10 representing "worst pain you can imagine". It takes less than 1 minute to complete. The NRS-11 is recommended as a core outcome measure of pain intensity for clinical trials in children and adults with NF1 (Wolters, 2016).

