8.1.6. Target Tumor Biopsy

For participants ≥ 18 years of age, a core needle or Tru-Cut needle biopsy of the target tumor will be performed at Baseline in the Treatment Phase prior to receiving any study treatment and after the MRI volumetric assessment has been confirmed evaluable by central radiologic review. This is a percutaneous biopsy method using a hollow-bored needle to obtain a volume of tissue in order to assess both cellular and architectural information. A 16-gauge needle or larger must be used. Fine needle aspirates are not acceptable. Participants 2 to 17 years of age should not undergo biopsy unless there is a clinical indication to obtain fresh tumor tissue. If a pediatric participant turns 18 years old during study participation, a biopsy is not required at the Cycle 24/Early Termination visit of the Treatment Phase. If a study biopsy was collected and the participant did not initiate study treatment, this biopsy may be utilized as the baseline biopsy if the participant subsequently re-screens for enrollment. If the participant did not have evaluable biopsy tissue at Baseline, they are not required to provide an End of Treatment biopsy of the target tumor.

Refer to Section 10.8 for the sampling schedule and the central laboratory manual for instructions for handling, processing and shipment of tumor biopsies.

8.1.7. 6-Minute Walk Test

Participants with a target PN that causes airway or lower extremity motor dysfunction will undergo a 6-Minute Walk Test in accordance with the SoA (Section 1.3) during the Treatment Phase. This assessment must always be completed after the Strength (Section 8.1.3) and Range

of Motion (Section 8.1.5) assessments. This evaluation should be performed by Rehabilitation Medicine, Physiatry, or Physical Therapy, if possible, and should ideally be completed by the same examiner at each visit, if feasible. Refer to the study reference manual for additional instructions.

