10.8. Appendix 8: Pharmacokinetic and Pharmacodynamic Sampling Schedule

	9	Day	Timepoint (hours post-dose)	PK sampling of PD-0325901 and metabolite (PD-0315209)	PD biopsy of target PN ^b
			0 (Pre-dose)	X a	X
	Cycle 1	1	1	X ^a	
	9		2	X a	
			0 (Pre-dose)	X a	
			0.5	X a	
	Cools 1	15	1	X a	
	Cycle 1	15	2	X a	
			3	X ^a	
			4	X ^a	
	Cycle 2	15	0 (Pre-dose)	X	
	Cycle 3	15	0 (Pre-dose)	X	
_	Cycle 4	15	0 (Pre-dose)	X	
Treatment Phase	Cycle 5	15	0 (Pre-dose)	X	
1 Hase	Cycle 6	15	0 (Pre-dose)	X	
	Cycle 7	15	0 (Pre-dose)	X	
	Cycle 9	15	0 (Pre-dose)	X	
	Cycle 11	15	0 (Pre-dose)	X	
	Cycle 13	15	0 (Pre-dose)	X	
	Cycle 15	15	0 (Pre-dose)	X	
	Cycle 17	15	0 (Pre-dose)	X	
	Cycle 19	15	0 (Pre-dose)	X	
	Cycle 21	15	0 (Pre-dose)	X	
	Cycle 23	15	0 (Pre-dose)	X	
	Cycle 24	21	0	X	X°
		Early Term	nination Visit		X ^c

Abbreviations: PD = pharmacodynamic; PK = pharmacokinetic;

Note: Actual drug dosing and PK sampling times must be documented by the Sites and will be captured in the database. It is important that PK sampling occurs as close as possible to the scheduled time. In order to achieve this, some of the other assessments scheduled at the same time need to be initiated prior to or after the time point to allow for completion of these measurements in enough time for the PK sampling to be taken at the designated time point. Thus, the sequence at a particular time point is: 1) vital sign measurements; 2) scheduled ECG 3); PK blood samples and 4) any other scheduled or unscheduled measurements at that time point.

^a Sampling window: Pre-dose collections should occur approximately within 1 hour prior to dosing. All post-dose timepoints have a ± 10 minute window. All efforts will be made to obtain the PK samples at the exact nominal time relative to dosing. However, samples obtained within the sampling window will not be captured as a protocol deviation if the exact time of the sample collection is noted on the source document and eCRF

b Percutaneous target PN core needle biopsies will be collected only from participants ≥ 18 years of age. When completed on the same visit, MRI must always precede a target PN biopsy.

^c End of Treatment Phase target PN biopsy will not be collected if the participant did not have a pre-dose target PN biopsy.

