4.1.2.2.2 Numerical Rating Scale=11 (NRS-11)

The NRS-11 is a self-report segmented 11-point numeric scale that assesses pain severity over the past 24 hours. The NRS-11 is administered daily over 7 consecutive days, inclusive of the study visit day, during the Treatment Phase as described in the SoA (Sections 1.3-1.4 of the protocol). For the ET visit, the assessment is only conducted once at the site and not for the preceding 6 days. Participants ≥ 8 years of age are administered the NRS-11 as a self-report.

Participants are asked to select the one number from 0 to 10 that best describes their worst pain over the past 24 hours for target tumor pain with 0 representing "no pain" and 10 representing "worst pain you can imagine". The NRS-11 score presented each visit will be taken as the average of the responses over the 7 consecutive days leading up to and including the visit day, with no transformation applied. The scale is presented in Appendix 1.3.

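### The protocol lets the adult baseline biopsy of the target tumor fall within the baseline pain diary, and neither the diary rules nor the SAP deals with the overlap

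*Protocol*

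**What the plan says.** **The biopsy.** Under inclusion criterion 6 (Protocol 5.1), participants aged 18 or over "must be willing to undergo pre-, and end of treatment tumor biopsies providing fresh tumor tissue". Section 8.1.6 requires a needle of 16 gauge or larger and says that the "biopsy of the target tumor will be performed at Baseline in the Treatment Phase prior to receiving any study treatment". The SoA marks it in the Baseline column, and the sampling schedule in Section 10.8 places it at Cycle 1 Day 1, pre-dose. A note there restricts it by age: "Percutaneous target PN core needle biopsies will be collected only from participants ≥ 18 years of age".

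**The permitted alternative.** SoA footnote 13 says: "This assessment may occur during the Screening period, but must be performed after the Screening MRI volumetric assessment has been confirmed evaluable". Footnote 3 and Table 7 repeat the allowance. The only other limit is that the biopsy precedes the first dose.

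**The diary.** Table 7 (Baseline and Cycle 1 Day 1) says: "The PII and NRS-11 questionnaires will be completed using the home ePRO device daily for 6 consecutive days prior to the scheduled Baseline visit". The visit-day entry makes seven, and at the visit itself PROs come before everything else. Screening lasts between 7 and 45 days.

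**The score.** The NRS-11 asks for the "worst pain over the past 24 hours for target tumor pain" (Protocol 8.1.2.2). SAP 4.1.2.2.2 says: "The NRS-11 score presented each visit will be taken as the average of the responses over the 7 consecutive days". SAP 4.1.2.2.3 averages the PII over the same days. The only rule that voids a visit score is for missing data: four or more of the seven readings absent (SAP 5.5.1.2 and 5.5.1.3).

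Neither document separates a Screening biopsy from the diary days, sets an interval between them, or says how affected entries are handled.

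**The concern.** The NRS-11 asks about the structure that has just been cored. Soreness on one or more diary days enters the baseline mean, and its resolution is then counted as a fall in pain. The trial is single-arm, so no comparator carries the same artifact. On-treatment diaries offer no offset: the second biopsy belongs to the Cycle 24 or Early Termination visit, where PROs again come first, and Cycle 13, the time point of interest for PROs (SAP 5.8), has no biopsy.

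The protocol guards against smaller disturbances. Strength and range-of-motion tests precede a blood draw that might affect them, sedation follows the functional tests, and MRI precedes biopsy at the end of treatment. A rule separating the Screening biopsy from the pain diary is missing from that set.

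At stake is the adult change from baseline in NRS-11 and PII, a secondary endpoint: the mean change, the MMRM and the proportion improved at Cycle 13. Baseline PedsQL and PGIS use a 7-day recall, so in principle they share the exposure, but less specifically, because neither asks about pain in the target tumor.

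**Working it through.** The plan gives no effect size, power or variability for the pain endpoint, so there is no figure to reproduce. The check covers timing, then size under stated assumptions.

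**1. Timing.** Six diary days precede the Baseline visit. Let S be the Screening length (7 to 45 days, Protocol) and r the days until central MRI confirmation (assumed). The share of permitted pre-visit days that are diary days is min(6, S − r)/(S − r).

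| S | r | Share |
|---|---|---|
| 7 | 1 | 6/6 = 100% |
| 21 | 7 | 6/14 = 43% |
| 45 | 14 | 6/31 = 19% |
| 45 | 1 | 6/44 = 14% |

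This is the share of available days, not of adults. A biopsy done at the Baseline visit after the PROs has no overlap at all.

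**2. One affected adult.** Let b be the extra NRS-11 points on each affected day and k the number of affected days (both assumed). If pain adds, the baseline rises by b × k/7.

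- b = 1, k = 2: 2/7 = 0.29
- b = 2, k = 3: 6/7 = 0.86
- b = 3, k = 3: 9/7 = 1.29

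To produce a false 1-point fall, b must be 7/k: 7.0 for one affected day, 3.5 for two, 2.33 for three. One affected day matters little.

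**3. Adult cohort mean.** Let f be the share of adults with overlap (assumed). The bias is f × b × k/7. With b = 2 and k = 3:

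- f = 25%: 0.25 × 0.86 = 0.21
- f = 50%: 0.50 × 0.86 = 0.43

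**4. Proportion improved.** SAP 6.11.2.3.1 uses a change of −1 or lower as one criterion. With no true change and normally distributed change scores, the share meeting it is Φ((−1 + shift)/SD). With an assumed SD of 2.0:

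- no shift: Φ(−0.50) = 30.9%
- shift 0.86: Φ(−0.07) = 47.2%

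Across the cohort, f = 25% gives 0.75 × 30.9 + 0.25 × 47.2 = 35.0%, and f = 50% gives about 39%. For an affected adult, an SD of 1.5 gives 25.2% rising to 46.3%, and an SD of 2.5 gives 34.5% rising to 47.8%.

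**5. Does the baseline covariate remove it?** The MMRM adjusts only for visit and baseline score. A single-visit simulation with baseline adjustment used 50 adults, half affected, b = 2, k = 3. Its assumptions were true pain with mean 4 and SD 2, error SD 0.8 at baseline and 1.2 at follow-up, and no true change. The adjusted mean change moved from −0.01 to −0.44. The shift passes through.

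**6. PII.** The same formula applies on its 0–6 scale. No figure is given because the documents offer nothing to anchor b.

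**The case against.** The default schedule already does the right thing. The SoA column, Section 8.1.6 and Section 10.8 all place the biopsy at Baseline, and PROs come first at that visit. Overlap needs a site to choose the Screening option and then to choose a diary day. A biopsy from an earlier screening attempt may also be reused. All of this stands, and it makes overlap a permitted option rather than the norm.

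A reader might infer that waiting for central MRI confirmation forces the biopsy late in Screening. The documents do not support that. Scans taken before consent are accepted if they fall within 45 days of first dose, so confirmation can come early. Only a Screening period near the 7-day minimum leaves little room.

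The sizes are assumptions, and the additive model is generous. A worst-pain score behaves more like a maximum: soreness of 4 in an adult already at 6 leaves 6. Respondents may also separate needle-site soreness from tumor pain, and analgesia after the biopsy could lower the baseline. This stands too: the direction is likely but not certain.

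The −1 criterion is one of two. The anchor-based threshold sits in a separate plan that is not available here, so misclassification against it is unknown. Both thresholds start from the same baseline, however.

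The study reference manual, which sets out the recommended order of assessments at each visit, might restrict timing. It is not available, and the protocol does not attribute such a rule to it.

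**Conclusion.** The gap is real and modest. The protocol permits the adult biopsy on home diary days, and the SAP averages those days without distinction. Under the assumption of 2 points on 3 of 7 days, added in full, an affected adult's baseline rises by 0.86, and the cohort mean by 0.21 to 0.43 if 25% to 50% of adults overlap. The bias is zero if no adult overlaps, and the documents do not give the true share.

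Three stronger readings are not supported:

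- That the artifact by itself turns an unchanged adult into an improver. On a full 7-day mean that needs, for example, at least 2.33 points on each of three days.
- That strength, range of motion and the 6-minute walk are exposed to the same degree. They are exploratory, limited to participants with relevant dysfunction, and nothing in the documents sizes an effect on them.
- That a planned comparison of adults with children is distorted. The cohorts are analyzed separately and no such test is planned, although an informal side-by-side reading would carry the adult-only artifact.

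ORR is unaffected. This is a cheap improvement to a secondary endpoint, not a threat to the trial's main conclusion.

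**What to change.** **Protocol (SoA footnotes 3 and 13, Table 7, Section 8.1.6).** State that the baseline research biopsy is done in one of two ways: at the Baseline visit, after the PROs and functional tests and before first dose; or in Screening, early enough that it falls neither within the 7-day diary nor shortly before it. The cost is slightly less scheduling freedom inside the 45-day Screening period.

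**SAP (Sections 6.11.2.3.1 and 6.11.2.3.2), for adults already enrolled.** Keep the baseline score as defined for the main analysis. Add a sensitivity analysis of NRS-11 and PII change (the MMRM and the proportion improved at Cycle 13) that omits adults whose biopsy fell within their baseline diary days, or within a short prespecified interval before them. Report how many there were. Do not count a biopsy done at the Baseline visit after the PROs as overlap. This needs only biopsy and diary dates, which I assume are recorded. The cost is a smaller adult sample in that one analysis.

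Do not simply drop every diary day on or after the biopsy. That would erase the whole baseline of an adult biopsied weeks earlier and delete a valid visit-day entry made before a Baseline-visit biopsy. Where four or more days were lost, it would also void the score under SAP 5.5.1.2 and 5.5.1.3, creating missing data in the endpoint it is meant to protect.

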1.4. Long-Term Follow-up Phase Schedule of Activities (SoA)

. Long-Term Follow	-up I hase senedule of Act	TVICIOS (SOLL)	
Cycle (LTFU)	Cycle 28 & Every 4 Cycles	End of Treatment (EOT) ¹⁷	Safety Follow- Up (SFU) ¹⁸
Cycle Day (Visit Window)	Day 15 (±5 d)		30 days (+5 days) after last dose of study treatment
Karnofsky/Lansky performance status criteria ¹	X	X	X
Weight/height ²	X	X	X
Physical examination	X	X	X
Vital signs ³	X	X	X
Laboratory			
Monthly urine pregnancy test ⁴ (WOCBP only)	$X \rightarrow (monthly)$	→X (monthly)	Х
Blood for hematology and serum chemistry ⁵	X	X	X
Urinalysis ⁵	X	X	X
Tumor Assessment	*		
MRI for tumor volume ⁶	X	X ^{6a}	
Other Clinical Assessments			
Ophthalmic assessments ⁷	X	X ⁷ a	X
12-Lead ECG ⁸	X	X	X
Echocardiogram ⁹	X	X^{9a}	X
Photography of PN ¹⁰	X	X	
PedsQL (paper) ¹¹	X	X	
P-OMAQ (paper) ¹²	X	X	
Study Treatment ¹²			
Study treatment dispensing ^{13a}	X		
Study treatment administration ^{13b}	X	X	
Study treatment accountability 13c	X	X	
Ongoing Monitoring			
Monthly wellness checks14	x→	→x	

Cycle (LTFU)	Cycle 28 & Every 4 Cycles	End of Treatment (EOT) ¹⁷	Safety Follow- Up (SFU) ¹⁸
Cycle Day (Visit Window)	Day 15 (±5 d)		30 days (+5 days) after last dose of study treatment
Concomitant medication review ¹⁵	x→	→	→x
AE / SAE review ¹⁶	x→	→	→x

AE = adverse event; d = day(s); ECG = electrocardiogram; EOT = end of treatment; IRT = interactive response technology; LTFU = Long-Term Follow-up; MRI = magnetic resonance imaging; PedsQL = Pediatric Quality of Life Inventory; PN = plexiform neurofibroma; P-OMAQ = Pediatric Oral Medicines Acceptability Questionnaire; SAE = serious adverse event; SFU = safety follow-up; WOCBP = women of childbearing potential

- Karnofsky/Lansky performance status scale can be found in Section 10.6. Participants will be assessed using the same scale utilized in the Treatment Phase.
- 2. Height/weight will be assessed to monitor body surface area (BSA) at applicable study visits to coincide with study treatment dispensing visits.
- 3. Vital signs (Section 8.2.3) are to include blood pressure, respiratory rate, pulse rate, and body temperature following at least 5 minutes of rest.
- 4. Pregnancy testing (Section 8.2.6) only required for women of childbearing potential (WOCBP). *Urine dipstick pregnancy tests will be conducted monthly during the LTFU Phase*. During the months when there is not a scheduled study visit, participants will be required to return to the Site for a urine pregnancy test, or if more convenient for the participant, they may visit a Sponsor approved local laboratory.
- Hematology, serum chemistry and urinalysis: Refer to Section 10.2 for a complete list of analytes and central laboratory manual for sample processing details. Microscopy is to be performed only as needed based on positive dipstick test results.
- Tumor volume of target PN will be measured by MRI (no contrast required) and all scans will be submitted for independent, blinded central radiologic review throughout the study.
 - 6a. MRI at End of Treatment (EOT) visit only required if not performed within the past 3 months.
- Ophthalmic assessments (Section 8.2.7) will include slit lamp with binocular indirect ophthalmoscopy and intraocular pressure measurements. Assessments must be performed by an ophthalmologist. Pediatric participants must be evaluated by a pediatric ophthalmologist.
 - 7a. Ophthalmic assessment at End of Treatment (EOT) visit only required if not performed within the past 3 months.
- 8. 12-Lead Electrocardiograms (ECGs) (Section 8.2.4) should be administered in triplicate (approximately 2-3 minutes apart and averaged) and read locally at the Site. Participants should rest in semi-recumbent supine position for at least 5 minutes prior to ECG collection.
- 9. Echocardiogram (Section 8.2.8): Left ventricular ejection fraction (LVEF) will be assessed via echocardiogram.
 - 9a. Echocardiogram at the End of Treatment visit only required if not performed within the past 3 months.
- 10. Photography of PN (Section 8.1.4) will be performed if target PN and/or its effects are visible and amenable to photography. Baseline photographs from the Treatment Phase should be present at the time of follow-up photography to allow for the most accurate positioning and setting replication. Photography assessment at the end of treatment (EOT) visit is only required if not performed within the past 3 months. Refer to study reference manual for details.
- 11. PedsQL (Section 8.1.2): Refer to Table 9 for the Age Range Scale. The study participant (and proxy, as applicable) will continue to complete the same form that was used in the Treatment Phase.
- 12. Pediatric Oral Medicines Acceptability Questionnaire (P-OMAQ) (Section 8.1.2.7): All participants that are utilizing the dispersible tablet (pediatric formulation) dosage form will complete the P-OMAQ (paper) self-report and caregivers will complete an observer report, as applicable. This assessment will only be conducted once

CONFIDENTIAL Protocol MEK-NF-201

Amendment 4 (17May2022)

for each participant and caregiver during the study. If this assessment was completed during the Treatment Phase, the assessment is not required to be completed in the LTFU phase.

- 13. Study treatment (Section 6):
 - 13a. Dispensing: Study treatment will be dispensed to participants using the IRT every 4 Cycles at scheduled study visits (as described in the SoA).
 - **13b. Administration:** Participants will self-administer study treatment orally on a twice daily (BID) dosing schedule of 2 mg/m² dose with a maximum dose of 4 mg BID. Dosing will be on a 28-day Cycle (4-week course) with a 3 week on/1 week off schedule.
 - **13c. Accountability:** Accountability will be performed by the Site personnel coinciding with each dispensing visit and recorded in the electronic case report form (eCRF).
- **Monthly wellness check-in** (Section 8.2.10): Monthly telephone or email contact is required throughout the study (may be replaced by a face-to-face interaction when study visits occur, and the information can be obtained during the visit).
- **15. Concomitant medications** Refer to Section 6.5.2 for prohibited or restricted medications.
- 16. Adverse events (AEs) and Serious Adverse Events (SAEs), which may include clinical laboratory test variables, will be monitored and documented from the time of informed consent/assent to 30 days after the last dose of study treatment. Refer to Section 8.3 for more detail.
- 17. End of Treatment visit will be conducted when a participant permanently discontinues study treatment for any reason and the participant should be encouraged to return to the Site to complete this visit as soon as possible. The EOT visit should be conducted as close to the last dose of study treatment as possible and every effort should be made to complete all procedures.
- 18. Safety Follow-Up (SFU) visit is required to be conducted 30 days (+5 days) after the last dose of study treatment. However, this visit is not required for participants who are transitioning directly to commercial mirdametinib at time of discontinuation (End of Treatment visit).

2. Introduction

Mirdametinib (PD-0325901) is an orally delivered, highly selective, small-molecule inhibitor of the dual specificity kinases, MEK1 and MEK2 (mitogen-activated protein kinase [MAPK]/ extracellular signal-regulated kinase [ERK]) that is being developed for the treatment of neurofibromatosis type 1.

Neurofibromatosis is classified into three major clinically and genetically distinct forms: neurofibromatosis types 1 and 2 (NF1 and NF2) and schwannomatosis. NF1, also known as von Recklinghausen disease, is the most common form of neurofibromatosis. NF1 is an autosomal dominant genetic disorder with an incidence of approximately 1 in 1900 to 2700 individuals (Uusitalo 2015, Evans 2010). Approximately one-half of cases are inherited with the remainder being the result of de novo mutations in the NF1 tumor suppressor gene, located at chromosome 17q11.2 (Evans 2010, Ledbetter 1989, Feldkamp 1998).

Neurofibromin, the protein product encoded by the NF1 gene, belongs to a family of guanosine triphosphate hydrolase (GTPase)-activating proteins (GAPs) that down-regulate the cellular proto-oncogene p21-ras (21 kD rat sarcoma viral oncogene homologs) (Martin 1990, Weiss 1999, Gutmann 2013). Ras activates numerous signaling pathways, including the MAPK pathways. Ras has been implicated in the control of cell growth and differentiation, and the ability of neurofibromin to down-regulate p21-ras suggests that the loss of neurofibromin may lead to uncontrolled cellular growth or tumor formation.

Mutations in the NF1 gene result in loss of production or reduced function of neurofibromin, causing the wide spectrum of clinical findings, including NF1-associated tumors (Shen 1996). Penetrance, or the likelihood that the individual carrying the mutation will manifest the disorder, is complete. The loss of neurofibromin in malignancy supports the notion that neurofibromin is a tumor-suppressor gene product.

NF1 is characterized by diverse, progressive cutaneous, neurological, skeletal and neoplastic manifestations with no standard drug treatment options available. The manifestation of the NF1 clinical diagnostic criteria typically appear in the order of café-au-lait macules, axillary and/or inguinal freckling, Lisch nodules (iris hamartomas), and finally neurofibromas (DeBella 2000). Most importantly, patients with NF1 develop both benign and malignant tumors at increased frequency throughout life (Gutmann 1997, Seminog 2013). Neurofibromas are the most common type of benign tumor that develops in patients with NF1 and occur in 20-50% of patients with NF1.

Neurofibromas are benign peripheral nerve sheath tumors that are comprised of a mixture of Schwann cells, fibroblasts, perineurial cells, and mast cells (Tucker 2011). When a neurofibroma extends longitudinally along a nerve and involves multiple fascicles, it is classified as a plexiform neurofibroma (PN). Plexiform neurofibromas rarely regress spontaneously, and in many patients their growth is relentless. Plexiform neurofibromas represent a major cause of morbidity and disfigurement in individuals with NF1, and when symptomatic, are associated

with increased mortality (Rasmussen 2001, Prada 2012). As tumor growth progresses, such lesions produce dysfunction, pain, and cosmetic disfigurement and can compress the airway or spinal cord. Furthermore, PNs have the potential to undergo malignant transformation producing malignant peripheral nerve sheath tumors (MPNSTs).

The approach to treatment of the various tumors associated with NF1 depends upon the type of tumor, its effect on adjacent tissues, and related complications. Plexiform neurofibroma usually involve multiple nerve fascicles, with serpiginous growth and significant vascularity. These lesions can be a significant challenge in surgical treatment and pain management, especially with progressive growth along the spinal column that may result in compression of the spinal cord (Gold 2013). The management of these complex lesions is unclear. In several series, patients were more likely to benefit from surgery when the indications were airway compression or disfigurement (Canavese 2011). However, up to 44% of tumors progress after the first surgery, most commonly in patients younger than ten years of age, with head and neck tumors that could not be completely resected (Needle 1997). Surgical resection often is limited to debulking of a specific area of a large lesion, for example, when a component is impinging on the spinal cord or airway or a large soft tissue component is removed to improve cosmesis. While no specific medical treatment for PNs exists, several therapies have been evaluated.

Clinical trials in patients with NF1 and associated PNs with the farnesyl transferase inhibitor tipifarnib (Widemann 2014), the mammalian target of rapamycin (mTOR) inhibitor sirolimus (Weiss 2014, Weiss 2015), and the fibroblast inhibitor pirfenidone (Widemann 2014b) have not demonstrated sufficient benefit to warrant clinical use. However, the placebo control arm of the tipifarnib study by Wideman et al (2014) reported a plexiform neurofibroma mean time-toprogression of 10.6 months and can serve as historical control group for phase 2 single-arm trials evaluating therapies in this population. Imatinib has resulted in shrinkage of PNs in a limited number of patients with NF1 and PNs (Robertson 2012, Jakacki 2011, Jakacki 2017). The most promising results have been obtained with selumetinib, an oral selective MAPK (MEK) inhibitor that was approved on April 13, 2020 for the treatment of pediatric patients ≥ 2 years with neurofibromatosis type 1 (NF1) who have symptomatic, inoperable PNs (Koselugo, 2020). Selumetinib was studied in a Phase 1 trial that enrolled 24 children with inoperable PNs (Dombi 2016). Children were treated for up to 56 months with selumetinib 20 to 30 mg/m² orally twice daily. All patients showed a decrease from baseline in the PN volume (median decrease 31%), and no patients had disease progression. A partial response, defined as a $\geq 20\%$ decrease in tumor volume from baseline for at least four weeks, was confirmed in 17 of 24 patients and was maintained for the duration of the study in 15 of 17 patients. Dose-limiting toxic effects included cellulitis, mucositis, urticaria, acneiform rash, elevated creatine kinase, and decreased left ventricular ejection fraction.

Additionally, a Phase 2 study (SPRINT) conducted by the same group of investigators, enrolled 50 patients aged 3-18 with inoperable morbid PNs. Using the same volumetric endpoint as the Phase 1 study, an independent centralized review of the final tumor response per REiNS criteria resulted in an objective response rate of 44% (95% CI: 30, 59) (Koselugo, 2020). Similar safety results were observed compared to the Phase 1 study. This trial also included individualized

functional assessments based on PN location. Between baseline and end of year 1 evaluations, parent and child-reported pain intensity and pain interference scores significantly improved (p < 0.01), as did strength (0-5 scale) and range of motion (degrees) of affected muscle groups/joints (p < 0.01) (Gross, 2018). Based on these data, selumetinib (KoselugoTM) was FDA-approved for the treatment of pediatric patients (2 years and older) with neurofibromatosis type 1 who have symptomatic inoperable plexiform neurofibromas in April of 2020.

